Study Duration	Estimated duration of the primary protocol (i.e., from completion of baseline to completion of follow-up) is 4 months
Study Center	University of Alaska Anchorage
Objectives	
 1. Develop a chatbot version of Step Away that delivers the interventions through an interactive format, and that proactively introduces the intervention features in a texting-based, narrative framework. 2. Conduct a pilot randomized controlled trial with a sample of problem drinkers (N = 150) to identify and compare differences in utilization and alcohol outcome efficacy between the Step Away chatbot, the Step Away app and a wait-list control condition. 3. Prepare for a larger RCT, the focus of which will be determined by the results from the pilot study. If one intervention demonstrates a clear superiority, it will be utilized in an RCT comparing it with usual care. If the effect size between groups is small to moderate, a larger RCT will be undertaken comparing the two interventions with a one-year follow up to determine differential effectiveness over time and moderators of effectiveness such as age, gender, alcohol dependence level and goal selection.
Number of Subjects	Approximately 150 randomized participants in 3 arms: app, chatbot, and delay (control)
Inclusion Criteria	
 • Are 18 years or older • Have an iPhone or Android phone • Are a U.S. resident • Are not in another form of alcohol treatment • Are actively drinking in the past 3 months • Have English language proficiency • Are not using another mHealth alcohol intervention • Score on the USAUDIT between an 8 to 24 for males under 65 • Score on the USAUDIT between a 7 to 24 for females and males over 65 on the USAUDIT
Study Product	Step Away app, Step Away chatbot

1. Schematic of Study Design

2. Key Roles

Principle Investigator

[name]
University of Alaska Anchorage
[name]
[name]
[contact]
[contact]

Co-Investigator

[name]
University of Alaska Anchorage
[name]
[name]
[contact]
[contact]

Project Manager

[name], MA
University of Alaska Anchorage
[name]
[name]
[contact]
[contact]

3. Introduction: Background Information and Scientific Rationale

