The interventions offered in this protocol, although self-administered and delivered via a novel mechanism (smartphones), are consistent in terms of content with interventions for alcohol problems that have research evidence for efficacy (e.g., Relapse Prevention). Further, similar self-administered interventions delivered via smartphone, bibliotherapy and the internet have been shown to be effective in substantially reducing alcohol intake. We have developed procedures to deal with the potential issue of exacerbation associated with participation in this study (see below).

In all studies to date of Step Away (2 with U.S. Veterans and one in New Zealand) and its prototype, the LBMI-A (performed at UAA in 2012), no adverse events have been reported.

4. Study Objectives and Purpose

This project will finalize development of the Step Away chatbot, which has been in process for over a year, and create an improved user interface for the Step Away app. We will then conduct a pilot study that compares three conditions, both Step Away interventions (i.e., smartphone app and chatbot) and a wait-list control condition that will receive the app after a 3-month delay. The trial focus will be on determining if the Step Away chatbot has better user engagement with regard to improved utilization of the features, enhanced intervention fidelity and improved alcohol outcomes compared to the Step Away app. Qualitative interviewing of 10 participants in each intervention group will identify perceptions of each intervention's usability and potential barriers to utilization.

Specific aims:

1. Develop a chatbot version of Step Away that delivers the interventions through an interactive format, and that proactively introduces the intervention features in a texting-based, narrative framework.
2. Conduct a pilot randomized controlled trial with a sample of problem drinkers (N = 150) to identify and compare differences in utilization and alcohol outcome efficacy between the Step Away chatbot, the Step Away app and a wait-list control condition.

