Phase II will entail a feasibility study that will contrast the Step Away chatbot with the Step Away app and a wait-list control condition, utilizing a randomized, controlled study design. A face-to-face control condition will not be utilized in this study as research has indicated that mobile health apps reach a different population of potential users whom we want to recruit for this study. A minimum of one hundred and fifty participants who are 18 years of age and older who screen positive for unhealthy alcohol use will be recruited throughout the U.S. with Facebook advertisements. All participants will complete an online, baseline research assessment and a follow-up at 4 months, allowing a minimum of 3 months of intervention use. Three months of intervention use will allow enough time for participants to utilize all aspects of the intervention system (the set-up phase), extended exposure to the daily assessment and weekly feedback functionality and provide a mid-length follow up period. Data from the app and chatbot usage will be continually uploaded to a secure server to determine usage and treatment fidelity information for each intervention. In addition, 10 participants in the chatbot and app conditions will be interviewed based on their degree of engagement with each intervention to obtain their perspectives on each intervention's usefulness and barriers to engagement. (At the 4-month

follow-up, all participants will be given the Substance Abuse and Mental Health Services Administration's (SAMHSA) national treatment locator helpline to identify treatment services in their area.)

Phase III will focus on quantitative and qualitative data analysis, manuscript development, conference presentations and preparation of a large-scale follow up grant.

All screening, baseline, and follow-up assessments will be performed online through Qualtrics.

Screening

All participants will be screened for eligibility. A copy of the screening questionnaire is available in the appendix.

Baseline

- The Timeline Followback (TLFB) will be used to gather information on alcohol and drug use. The TLFB will be used to calculate the following drinking variables: average (mean) drinks per week, days abstinent, and heavy drinking days. Heavy drinking days will be defined as days with 4 or more standard drinks for women and 5 or more standard drinks for men.
- Short Inventory of Problems – Revised (SIP-R) will be used to assess the adverse consequences of substance use.

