- The treatment history section of the Form 90 will be modified to be administered online at baseline and follow-up, to gather lifetime treatment history, self-help attendance, and treatment use.
- Readiness to Change. We will utilize the Readiness to Change Treatment Version (RCQTV), which RCQTV has been shown to have solid reliability and validity and has been modified for individuals contemplating or engaged in treatment for alcohol problems.

Follow-Up

The US AUDIT, TLFB, SIP-R, and Readiness to Change questionnaires will be used for the follow-up assessments. In addition, those in the app and chatbot groups will be asked to complete the System Usability Scale to assess their perceptions of the interventions' usability. The follow-up survey will be sent to participants at 4 months post-enrollment.

Interviews

Interviews will be conducted after the completion of the follow-up survey. Interview questionnaires will focus on users' experiences with the app or the chatbot. These interviews will be conducted over the phone.

8. Assessment of Safety

Several safety measures will be put in place to ensure the safety, comfort, and confidentiality of all participants. Care will be taken to inform potential participants fully before they consent to participate about all potential risks that may arise from their participation. The two most important aspects of participant protection in the proposed work are assuring the adequacy of informed consent (including full disclosure of all potential risks) and protecting confidentiality. To minimize risk, we will clearly explain all procedures to participants in our informed consent documents and clearly outline safeguards for confidentiality implemented in the study. Further, in order to protect their confidentiality, all participants will be encouraged to set a password to access their smartphone home screen.

Also, a Data Safety Monitoring Board (DSMB) will be convened in Year 1 of the project and will include the following two members with expertise in psychology, behavioral health, and

research ethics. The DSMB will meet twice during each year of the project to review the status of the project.

9. Statistical Considerations

All randomized study participants who complete both the baseline and follow-up surveys will be the primary population for the analysis. Three subgroups will be analyzed: the app group, the chatbot group, and the delay group.

Outcomes, Statistical Methods, and Statistical Analyses

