All outcomes will be presented using descriptive statistics. Binary and categorical variables will be presented using counts and percentages. SPSS 27 will be used for all statistical analyses.

Research Question 1: Do participants reduce their alcohol consumption more when using the app or the bot?

Hypothesis 1: Participants using either the app or bot will show a significantly greater reduction in alcohol consumption and alcohol related problems than participants in the delay group.

Method: Repeated Measures Anova

Baseline and Follow-up data from the Alcohol Use Disorder Identification Test (USAUDIT), Short Inventory of Problems-Revised (SIP-R), Readiness to Change Questionnaire (RTCQ), and Timeline Followback (TLFB) will be compared between app, chatbot, and delay groups. Consumption data used from the TLFB will include drinks per day, percentage of days abstinent, and heavy drinking days. Average drinks per day will be calculated from the reported last 14 days of drinks. Percentage of days abstinent will be calculated as the percentage of days in the recent 14 days that participants reported 0 drinks. Heavy drinking days will be calculated as the number of days in the past 14 days that participants report drinking more than 3 drinks if they are an assigned female at birth or 4 drinks if they are an assigned male at birth. Repeated measures ANOVA will be ran to identify if there is an interaction between time and group. An interaction would indicate a significant difference between app, bot, and delay groups in the difference of their baseline and follow-up drinking data.

Research Question 2: Do participants utilize the app and bot differently?

Hypothesis 2: Participants in the bot group will utilize the intervention significantly more than the app group due to the intervention's conversational interface.

Method: Independent sample t-test

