Consent and Other Informational Documents Provided to Participants

Copies of the consent documents, emails, and other outreach to participants are provided in the Appendix.

Consent Procedures and Documentation

A brief overview will tell participants who is conducting the research study, and that it involves trying out a program to address unhealthy alcohol use that involves a program delivered over their smartphone. They will be told that if they want to join the study they will be placed in one of three groups, and that all groups will be of no cost to them and that all programs will also ask them to do activities on their phone to help them manage their drinking. Also, they will be told that no matter which group they are in, they will be asked to complete electronic surveys two times during the study and will possibly be asked to participate in a short interview at the end of the study. They will also be informed that [name] has a financial interest in the company, Here and Now Systems, LLC that owns the Step Away intervention and that results may inform future versions as commercial products. They will be informed that [name] will not be involved in data management and analysis within this study and that those procedures will be performed by the UAA Center for Behavioral Health Research and Services (CBHRS) under the supervision of [name]. They would then be asked to click ‘yes’ if they are interested and would like to be screened to see if the study is right for them. If they assent to be screened,

they will be first told that all information they provide will be kept private, and that they can exit at any time. They will then electronically be asked all screening questions and an eligibility determination will be made and communicated to them. Those who are ineligible or who decide not to participate will be offered referrals to other substance abuse treatment services in the community.

Eligible and interested participants will then undergo an electronic informed consent (eIC) process, following guidance for Institutional Review Boards, Investigators, and Sponsors, described in a 2016 Procedural co-authored by the US Department of Health and Human Services (DHHS), Office for Human Research Protections (OHRP), Center for Drug Evaluation and Research, and other federal agencies (www.fda.gov/downloads/drugs/guidances/ucm436811.pdf).

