The eIC will contain all elements of a paper informed consent, will be written at an 8th grade or below reading level, and will include questions to gauge the participants understanding of the project purpose, risks, key study elements, and their right to withdraw without penalty, at any time throughout the study. Incorrect answers to questions related to the eIC elements will highlight areas where participants may need further explanation and will prompt a call from study staff to answer questions. Participants can also request a call to discuss the content of the consent prior to electronically signing. It should be noted that OHRP permits electronic signatures if such signatures are legally valid within the jurisdiction where the research is to be conducted (in this case, Alaska). [name] will discuss all plans for using eIC with UAA's IRB before finalizing the eIC development, to assure it complies with institutional, state and federal regulations.

After completion of informed consent, participants will complete baseline assessments via the website. Following baseline assessment completion, participants will be randomly assigned to either chatbot or app versions of StepAway, or a waitlist to app, using a blinded, computer-generated random assignment code. This process will be repeated until at least 50 eligible participants are enrolled in each study arm.

In addition to the eIC that each enrolled participant completes at the outset of the study, each participant who agrees to participate in an interview will be provided with additional consent specific to the interview. As these will be done over the phone with participants who live across the United States, verbal consent will be requested and documented.

Participant and Data Confidentiality

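### The delay arm is due to get the app at 3 months but its only follow-up is sent at 4 months, so the control drinking data for Hypothesis 1 can fall after app access opens

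*Combined protocol and SAP*

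**What the plan says.** - **Delay-arm access.** Section 4 describes a "wait-list control condition that will receive the app after a 3-month delay". This is the only visible place that gives the length of the delay, and it does not say when the 3 months begin.
- **Randomization.** Section 10 (Consent Procedures and Documentation): "Following baseline assessment completion, participants will be randomly assigned to either chatbot or app versions of StepAway, or a waitlist to app".
- **Follow-up.** Section 7 (Follow-Up): "The follow-up survey will be sent to participants at 4 months post-enrollment". No timing specific to an arm is given. The synopsis puts the primary protocol at 4 months, counted "from completion of baseline to completion of follow-up) is 4 months". Sections 5 and 7 describe "a follow-up at 4 months, allowing a minimum of 3 months of intervention use".
- **Number of surveys.** Section 10 tells participants that "they will be asked to complete electronic surveys two times during the study", so there is one baseline and one follow-up.
- **Outcome window.** Section 9 (Research Question 1): "Average drinks per day will be calculated from the reported last 14 days of drinks". Percentage of days abstinent and heavy drinking days use the same 14-day span.
- **Contrast.** Hypothesis 1 in Section 9 is that app or bot users "will show a significantly greater reduction in alcohol consumption and alcohol related problems than participants in the delay group", tested by a time-by-group interaction across the three groups. The analysis population is everyone who completes both surveys. No rule covers delay-arm app use before the follow-up.

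**The concern.** A wait-list arm serves as a no-intervention comparator only while its members are still waiting when the outcome is measured. On the dates given, the controls may have had the app for a month when their only follow-up survey is sent. There is no earlier post-baseline survey to fall back on.

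If controls use the app before or during the 14-day window, Hypothesis 1 no longer compares intervention with none. It compares earlier with later access, and the difference is likely to be biased toward zero. A null result could not then be interpreted. An early effect in controls is plausible but cannot be sized: the only evidence on speed in the documents is the 6-week prototype pilot in Section 3, in people with an alcohol use disorder.

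The problem is confined to contrasts with the delay arm. The chatbot-versus-app comparison, Hypothesis 2 and the choice between the two interventions under Aim 3 do not depend on it.

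**Working it through.** **Inputs from the documents.** Delay to access: 3 months (Section 4). Survey sent: 4 months post-enrollment (Section 7). TLFB window: 14 days (Section 9). The month length, access lag and return lag are not given, so each is varied below.

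**Step 1: both clocks start at enrollment.** Let A be the day access opens and F the day the survey is sent. The window opens on day F − 14, so the time from access to window opening is F − 14 − A.

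| Month convention | A | F | F − 14 − A |
|---|---|---|---|
| Calendar months | 91 | 122 | 17 days |
| 30-day months | 90 | 120 | 16 days |
| 4-week months | 84 | 112 | 14 days |

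Under every convention, all 14 TLFB days fall after access opens.

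**Step 2: the delay clock starts later, or the survey comes back late.** Let L be the lag before the 3-month clock starts and r the days from sending to return. The number of window days on or after the opening of access is

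max(0, min(14, F + r − A − L)).

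Example with calendar months, L = 21, r = 0: 122 − 91 − 21 = 10 days.

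Days out of 14 that fall after access (range over the three conventions):

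| Access lag L | Returned same day | Returned 7 days later | Returned 14 days later |
|---|---|---|---|
| 0–14 days | 14 | 14 | 14 |
| 21 days | 7–10 | 14 | 14 |
| 28 days | 0–3 | 7–10 | 14 |
| Full month (28, 30 or 31 days) | 0 | 7 | 14 |

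On the stated dates, then, the window is clear only with a lag of about a month and prompt return.

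**Step 3: what can be dated.** USAUDIT and SIP-R are collected at the same survey, but no look-back period is stated for them at follow-up. Their overlap with access cannot be calculated.

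**Step 4: consequence for power (illustration only).** The target of 50 per arm cannot be reproduced, because Section 6 gives no alpha, power, effect size or standard deviation. The following are therefore assumptions: standardized effect d, two-sided alpha 0.05, two-sample t-test, 50 per arm, and controls gaining a fraction a of the effect. The effective difference is d(1 − a), with noncentrality d(1 − a) × √(50/2) = 5d(1 − a). For d = 0.5 and a = 0.25 the effective difference is 0.375 and the noncentrality is 1.875, which gives 46% power.

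| Assumed d | a = 0 | a = 0.25 | a = 0.5 |
|---|---|---|---|
| 0.3 | 32% | 20% | 12% |
| 0.5 | 70% | 46% | 24% |
| 0.8 | 98% | 84% | 51% |

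**The case against.** The strongest reply is that the overlap rests on something the plan leaves unsaid. Section 4 gives no start for the 3 months. Sections 5 and 7 fit at least 3 months of use inside a 4-month follow-up, which suggests up to a month of start-up slack. If the delay clock had that slack and surveys came back on the day they were sent, no TLFB day would fall after access. Some appendix pages were not available for this review, and the visible check-in script shows that app instructions go out by dated email, so a release rule could sit there. All of this stands, and it is why the finding is that the window can fall after access, not that it must. But the slack is described for intervention use, not for the delay arm's clock, and no visible text holds access until the survey is returned.

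Access is also not use. The same script provides for participants who have not downloaded the app, and Section 3 names sustained engagement as a limitation. The day counts are therefore an upper bound on exposure. The return lags of 7 and 14 days are assumed, and they run past the 4-month completion estimated in the synopsis.

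The power figures depend on assumed inputs and a simpler test than the planned repeated measures ANOVA. If d = 0.5 is on the raw scale and the baseline to follow-up correlation is assumed to be 0.7, a change-score analysis gives 89%, 67% and 36% in place of 70%, 46% and 24%. The levels move but the direction does not. The case for a change rests on the dates, not on these percentages.

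Finally, this is a pilot focused on chatbot versus app, and bias toward no difference is unlikely to produce a false claim of efficacy. That limits the damage. It does not rescue Hypothesis 1, which is stated only against the delay group.

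**Conclusion.** The concern holds on the text as written. If both clocks run from enrollment, delay-arm access opens 14 to 17 days before the TLFB window, and 14 of 14 control days fall after it. A later start to the delay clock reduces the count, to zero at about a full month with same-day return. A two-week late return restores all 14 days even then.

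The likely effect is bias toward zero in both contrasts with the delay group. Its size cannot be computed from the documents, because it depends on how many controls take up the app and how quickly it works. This must be fixed because Hypothesis 1 relies wholly on that arm, and an uncontaminated control measurement cannot be recovered once access has opened. Confidence is medium, given the unstated clock start and the unavailable appendix pages.

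**What to change.** 1. Reconcile Section 4 with Sections 5, 7 and 9. State the event that starts the 3-month clock.
2. Order the dates so that each participant's follow-up survey, and with it the 14-day window, closes before delay-arm access opens. Judge this by survey return or a stated closing date, not by the sending date. Keep survey timing the same in all arms. Which date moves is the sponsor's choice.
3. If neither date can move, label the contrast as immediate versus delayed access and report server-logged delay-arm app use before the survey.
4. Separately, settle what the control is. Section 5 describes an app limited to assessment and feedback, whereas Sections 4, 7 and 10 describe a wait-list and the synopsis a delay arm.

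**Cost.** Protocol wording and a change to the survey or access trigger, with no extra participants or assessments. The price is either later delay-arm access, by about a month plus survey-return time, or an earlier survey that uses up the slack behind the 3-month minimum of use. The fallback in item 3 relies on usage data that the plan already uploads.

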3. Prepare for a larger RCT, the focus of which will be determined by the results from the pilot study. If one intervention demonstrates a clear superiority, it will be utilized in an RCT comparing it with usual care. If the effect size between groups is small to moderate, a larger RCT will be undertaken comparing the two interventions with a one-year follow up to determine differential effectiveness over time and moderators of effectiveness such as age, gender, alcohol dependence level and goal selection.

5. Study Design

This study will consist of three phases. Phase I will focus on developing the AI chatbot version of Step Away, improving the Step Away app and developing procedures for the pilot study, including evaluating the different program elements using an expert panel. Phase II will entail a feasibility study that will contrast the Step Away chatbot with the Step Away app and an assessment and feedback-only app (the first step of the Step Away app but nothing else) utilizing a randomized, controlled study design. One hundred and fifty participants who are 18 years of age and older who screen positive for unhealthy alcohol use will be recruited throughout the U.S. with Facebook and Google ads. All participants will complete an online, baseline research assessment and a follow-up at 4 months, allowing a minimum of 3 months of intervention use. Three months of intervention use will allow enough time for participants to utilize all aspects of the intervention system (the set-up phase), extended exposure to the daily assessment and weekly feedback functionality and provide a mid-length follow up period. Data from the app and chatbot usage will be continually uploaded to a secure server to determine usage and treatment fidelity information for each intervention. In addition, 10 participants in the chatbot and app conditions will be interviewed based on their degree of engagement with each intervention to obtain their perspectives on each intervention's usefulness and barriers to engagement. (At the 4-month follow-up, all participants will be given the Substance Abuse and Mental Health Services Administration's (SAMHSA) national treatment locator helpline to identify treatment services in their area.) Phase III will focus on quantitative and qualitative data analysis, manuscript development, conference presentations, revisions to StepAway intervention based on findings

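### Section 5 names a different control arm from the rest of the protocol, and under the wait-list version the delay arm is probably measured after it already has the app

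*Combined protocol and SAP*

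**What the plan says.** **Section 5, Study Design.** The chatbot and the app are contrasted with "an assessment and feedback-only app (the first step of the Step Away app but nothing else".

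**Everywhere else the arm is described:**
- Synopsis, Number of Subjects: "Approximately 150 randomized participants in 3 arms: app, chatbot, and delay (control".
- Section 4: "a wait-list control condition that will receive the app after a 3-month delay". This is the only place that gives the length of the delay.
- Section 6, Target Sample Size: the third group is called the delay group.
- Section 7, in a sentence that otherwise closely parallels the one in Section 5: "contrast the Step Away chatbot with the Step Away app and a wait-list control condition".
- Section 9, Hypothesis 1: app or chatbot users will show a "significantly greater reduction in alcohol consumption and alcohol related problems than participants in the delay group".
- Section 10, Consent Procedures and Documentation: participants are "randomly assigned to either chatbot or app versions of StepAway, or a waitlist to app".

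**What participants are told.** The overview in Section 10 says of all three groups that "all programs will also ask them to do activities on their phone to help them manage their drinking".

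**Timing of the outcome.** Section 7, Follow-Up: "The follow-up survey will be sent to participants at 4 months post-enrollment". Section 10 counts two electronic surveys per participant, so there is no other outcome assessment. Section 9 computes drinks per day, percentage of days abstinent and heavy drinking days from the last 14 days.

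**The concern.** There are two separate problems.

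First, a feedback-only app and a wait-list are different comparators. Against a wait-list, the trial estimates the effect of offering Step Away now rather than later. Against a feedback-only app, it estimates what the remaining steps add to assessment and feedback. Nothing in the documents says that the wait-list arm gets the feedback step while it waits, so the two descriptions cannot be merged.

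Second, and more important, the wait-list version has a timing conflict of its own. Controls are released to the app at 3 months and everyone is surveyed at 4. If release comes before the 14-day window opens, the delay arm's drinking is recorded while it has the intervention under test. Any benefit controls draw from it is subtracted from the effect in Hypothesis 1. With no earlier survey of that arm, the analysis cannot recover the comparison with no access.

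**Working it through.** **1. The plan's own figure.** 3 arms × 50 = 150, which agrees with the stated total. The 50 per arm cannot be derived, because no alpha, power, effect size or SD is given. The power sentence speaks only of modest pre-to-post effects.

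**2. Count of descriptions.** One place (Section 5) says feedback-only app. Six places (synopsis, Section 4, sample size, Section 7, Hypothesis 1, randomization) say delay or wait-list. The last two govern analysis and allocation.

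**3. Timeline of the delay arm.** Inputs: 3-month delay (Section 4), survey at 4 months post-enrollment (Section 7), 14-day look-back (Section 9). Assumptions: 30-day months and a survey completed on time. Let *s* be the number of days from enrollment to the start of the delay, which the documents do not state.

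- Release: day 90 + *s*
- Survey: day 120
- Window opens: 120 − 14 = day 106
- Access before the survey: 120 − (90 + *s*) = 30 − *s* days

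| Delay starts (*s*) | Release | Delay-arm access before survey | 14-day window |
|---|---|---|---|
| 0 days | day 90 | 30 days | wholly after release |
| 16 days | day 106 | 14 days | wholly after release |
| 23 days | day 113 | 7 days | half after release |
| 30 days | day 120 | 0 days | wholly before release |

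The window is clear of access only if the delay starts a full month after enrollment. A late survey adds days of access in every row. With *s* near 0, and the active arms also given access at about enrollment, the contrast is about 4 months of access against about 1.

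**4. Direction of the bias.** Let *D* be the effect of full access against no access, and *f* the share of *D* that controls have gained by follow-up. The contrast is then *D*(1 − *f*), which is smaller than *D* for any *f* between 0 and 1.

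**5. Illustration of size.** Assumptions, none from the documents: *D* = 0.5 SD of change, two-sided alpha 0.05, 50 per arm, no dropout, one active arm against the delay arm.

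Power ≈ Φ(*d*·√(50/2) − 1.96) = Φ(5*d* − 1.96). Number per arm for 80% power = 2(1.96 + 0.84)²/*d*², about 15.7/*d*².

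| *f* | *d* = 0.5(1 − *f*) | 5*d* − 1.96 | Power at 50 per arm | Per arm for 80% |
|---|---|---|---|---|
| 0 | 0.50 | 0.54 | 70% | 63 |
| 0.25 | 0.375 | −0.085 | 47% | 112 |
| 0.50 | 0.25 | −0.71 | 24% | 252 |

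The same arithmetic would apply if the control were the feedback-only app, with *f* the share of the effect produced by feedback. The planned test is a three-group repeated-measures ANOVA on completers, so these are not the trial's actual power figures.

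**The case against.** **The Section 5 phrase may be leftover text.** Section 7 closely parallels that sentence with the comparator changed, and Hypothesis 1 names the delay group. A reader might infer that the comparator for Hypothesis 1 is undefined. The documents do not support that: every text governing allocation or analysis says delay or wait-list. Nor do they confirm that the phrase is a remnant, so it still has to be corrected.

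**The timing depends on an unstated start point.** Sections 5 and 7 say the 4-month follow-up allows at least 3 months of use, which leaves room for access to begin up to a month after enrollment. If the delay is counted from such a late start, release could fall at month 4 and the overlap would vanish. Access is also not the same as use. This stands, so contamination is likely rather than proven. Against it, assignment follows directly on the baseline assessment, and the synopsis counts 4 months from completion of baseline to completion of follow-up. A start close to enrollment is therefore the natural reading.

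**The consent sentence can fit a wait-list**, since that arm also receives a phone program eventually. A reader might infer that participants are misinformed. The overview in Section 10 does not establish that, and the consent form itself is not in the copy reviewed. It warrants a check only.

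**Much of the trial is untouched.** A reader might infer that the pilot cannot serve Aim 3. That goes too far. The Aim 3 rule turns mainly on whether one intervention is superior to the other, and Hypothesis 2 compares only app and chatbot. The contrast with the delay group is what suffers.

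**Conclusion.** The point holds in two parts. Section 5 contradicts the other descriptions of the third arm and must be reconciled with them; this is an inconsistency in current text, with the wait-list the better-supported version. Under that version, if the delay begins within about 16 days of enrollment and the survey is on time, all 14 days of the delay arm's TLFB window fall after app release. Between 16 and 30 days the overlap is partial, and at 30 days it is nil. In the first case Hypothesis 1 compares early with late access rather than access with none, and its contrast with control is likely biased toward the null, to the extent that controls use and benefit from the app. The amount cannot be computed from the documents, and the power figures only illustrate the direction and rough scale. The app-versus-chatbot comparison is not affected. This should be corrected before follow-up, because an outcome measured after release cannot be restored by analysis.

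**What to change.** 1. Replace the comparator phrase in Section 5 so that it matches the arm actually randomized, and state in one place what that arm receives and when.
2. Check that the consent overview in Section 10, and the form based on it, describe that arm correctly.
3. State the event from which the 3-month delay is counted (enrollment, baseline completion, randomization or another).
4. Reconcile the release time in Section 4 with the survey time in Section 7, so that each delay-arm participant completes the outcome assessment before receiving the app. Keep the assessment time equal in all three arms: surveying only the delay arm earlier would replace exposure bias with unequal follow-up.
5. Record the dates of release, first use and survey for each delay-arm participant, so that any overlap can be reported.

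Cost: an IRB amendment to wording, and about one month's shift in either delay-arm access or the survey. Later access means a longer wait for controls. An earlier survey, applied to all arms, shortens exposure in the active arms and would have to be squared with the stated minimum of 3 months of use. Sample size and analysis method need not change for this point.
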